Attachment 2 DETAILED PROHIBITED CHANGES IN UC MEDICATIONS RULES

Participants who had a prohibited change in UC medication described below are considered to have ICE 3:

- Initiation of prohibited medications or therapies as defined in the protocol (see protocol Section 6.5.2).
- Initiation of restricted medications (rectal 5-ASA compounds; parenteral or rectal corticosteroids, including budesonide and beclomethasone dipropionate).
- Increase in the dose of oral corticosteroids (excluding budesonide and beclomethasone dipropionate) > 5 mg/day (prednisone equivalent) above the maintenance baseline dose for more than 7 days after the maintenance baseline visit due to worsening of disease. This includes initiation of oral corticosteroids due to worsening of disease that lasts for more than 7 days after the maintenance baseline visit for participants who were not receiving oral corticosteroids at maintenance baseline.
- Increase in the dose of oral budesonide > 3 mg/day above the maintenance baseline dose for more than 7 days after the maintenance baseline visit due to worsening of disease. This includes initiation of oral budesonide due to worsening of disease that lasts for more than 7 days after the maintenance baseline visit for participants who were not receiving oral budesonide at maintenance baseline.
- Increase in the dose of oral beclomethasone dipropionate > 5 mg/day above the maintenance baseline dose for more than 7 days after the maintenance baseline visit due to worsening of disease. This includes initiation of oral beclomethasone dipropionate due to worsening of disease that lasts for more than 7 days after the maintenance baseline visit for participants who were not receiving oral beclomethasone dipropionate at maintenance baseline.
- Increase in the dose of oral corticosteroids (excluding budesonide and beclomethasone dipropionate) > 5 mg/day (prednisone equivalent) above the maintenance baseline dose for more than 28 days after the maintenance baseline visit due to reasons other than worsening of disease. This includes initiation of oral corticosteroids due to reasons other than worsening of disease that lasts for more than 28 days after the maintenance baseline visit for participants who were not receiving oral corticosteroids at maintenance baseline.
- Increase in the dose of oral budesonide > 3 mg/day above the maintenance baseline dose for more than 28 days after the maintenance baseline visit due to reasons other than worsening of disease. This includes initiation of oral budesonide due to reasons other than worsening of disease that lasts for more than 28 days after the maintenance baseline visit for participants who were not receiving oral budesonide at maintenance baseline.
- Increase in the dose of oral beclomethasone > 5 mg/day above the maintenance baseline dose for more than 28 days after the maintenance baseline visit due to reasons other than worsening of disease. This includes initiation of oral beclomethasone dipropionate due to reasons other than worsening of disease that lasts for more than 28 days after the maintenance baseline visit for participants who were not receiving oral beclomethasone dipropionate at maintenance baseline.
- Any switch among oral budesonide, oral beclomethasone dipropionate or other oral corticosteroids (excluding prednisone equivalent changes) due to worsening of disease.

- Statistical Analysis Plan CNTO1959UCO3001 Amendment 2
- Initiation of oral 5-ASA compounds due to worsening of disease.
- Increase above maintenance baseline in the dosage of oral 5-ASA compounds due to worsening of disease.
- Change from one oral 5-ASA compound to another 5-ASA compound due to worsening of disease.
- Initiation of 6-MP/AZA/MTX due to worsening of disease.
- Increase above maintenance baseline in the dosage of 6-MP/AZA/MTX due to worsening of disease.
- Any switch between 6-MP/AZA and MTX due to worsening of disease.

Attachment 3 Grading Criteria for the histological evaluation of Disease Activity in Ulcerative Colitis (Geboes grading system3)

Grade 0	Structural (architectural change)
Subgrades	
0.0	No abnormality
0.1	Mild abnormality
0.2	Mild or moderate diffuse or multifocal abnormalities
0.3	Severe diffuse or multifocal abnormalities
Grade 1	Chronic inflammatory infiltrate
Subgrades	
1.0	No increase
1.1	Mild but unequivocal increase
1.2	Moderate increase
1.3	Marked increase
Grade 2	Lamina propria neutrophils and eosinophils
2A Eosinophils	
2A.0	No increase
2A.1	Mild but unequivocal increase
2A.2	Moderate increase
2A.3	Marked increase
2B Neutrophils	
2B.0	None
2B.1	Mild but unequivocal increase
2B.2	Moderate increase
2B.3	Marked increase
Grade 3	Neutrophils in epithelium
3.0	None
3.1	< 5% crypts involved
3.2	< 50% crypts involved
3.3	> 50% crypts involved
Grade 4	Crypt destruction
4.0	None
4.1	Probable-local excess of neutrophils in part of crypt
4.2	Probable-marked attenuation
4.3	Unequivocal crypt destruction
Grade 5	Erosion or ulceration
5.0	No erosion, ulceration, or granulation tissue
5.1	Recovering epithelium+adjacent inflammation
5.2	Probable crosion-focally stripped
5.3	Unequivocal erosion
5.4	Ulcer or granulation tissue

[figure not shown]

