 - 11.1 Stool culture or other examination positive for an enteric pathogen, including *Clostridium difficile* toxin, within 4 months before the first dose of study intervention, unless a repeat examination is negative and there are no signs of ongoing infection with that pathogen. Note: If time allows, treatment and repeat testing can occur in the current screening period.

Concomitant or previous medical therapies received

12. Has received the following prescribed medications or therapies:
 - a. A biologic therapy targeted at IL-12 and/or IL-23 (eg, ustekinumab, briakinumab, guselkumab, mirikizumab, tildrakizumab, brazikumab, or risankizumab).
 - b. Natalizumab within 12 months of the first dose of study intervention.
 - c. Agents that deplete B or T cells (eg, rituximab, alemtuzumab) within 12 months of the first dose of study intervention or continue to manifest depletion of B or T cells more than 12 months after completion of therapy with lymphocyte-depleting agents.

- d. Any investigational drug/therapy within 4 weeks before the first dose of study intervention or within 5 half-lives of the investigational agent, whichever is longer.
- e. Apheresis (eg, Adacolumn or Cellsorba apheresis) within 2 weeks before the first dose of study intervention.
- f. Fecal microbiota transplantation within 12 weeks before the first dose of study intervention.

Infections or predisposition to infections

13. History of latent or active granulomatous infection, including histoplasmosis or coccidioidomycosis, before screening. Refer to Inclusion Criterion #12 for information regarding eligibility with a history of latent TB.
14. History of, or ongoing, chronic or recurrent infectious disease, including but not limited to, recurrent sinopulmonary infections, bronchiectasis, recurrent renal/urinary tract infection (eg, recurrent pyelonephritis, recurrent cystitis), an open, draining, or infected skin wound, or an ulcer.
15. Chest radiograph within 12 weeks before the first dose of study intervention that shows an abnormality suggestive of a malignancy or current active infection, including TB.
16. History of being human immunodeficiency virus (HIV) antibody-positive, or tests positive for HIV at screening.
17. Criterion modified per Amendment 2.
 - 17.1. Is seropositive for antibodies to hepatitis C virus (HCV), unless they satisfy 1 of the following conditions:

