6.5. Concomitant Therapy

Prestudy therapies administered up to 30 days before the first dose of study intervention must be recorded on the eCRF. Any COVID-19 vaccines administered, regardless of timing, must be recorded on the eCRF. Concomitant therapies must be recorded throughout the study, from signing of the informed consent to the last study visit.

All therapies (prescription or over-the-counter medications, including vaccines, vitamins, herbal supplements; non-pharmacologic therapies such as electrical stimulation and acupuncture) different from the study intervention must be recorded in the eCRF.

Recorded information will include a description of the type of therapy, treatment period, dosage, route of administration, and indication. Modification of an effective pre-existing therapy should not be made for the explicit purpose of entering a participant into the study.

Participants who are receiving oral 5-ASA compounds, oral corticosteroids, 6-MP, AZA, or MTX for the treatment of UC at baseline (ie, Week I-0) should maintain a stable dose for the specified period before baseline, as defined in the Inclusion Criteria (Section 5.1).

In general, participants who are receiving these medications for UC at baseline of either Induction Study 1 or Induction Study 2 (ie, Week I-0) should maintain a stable dose through Week M-44, except for oral corticosteroids. Therapies can only be discontinued or reduced in dose after Week I-0 if investigator judgment requires it because of toxicity or other medical necessity; even if the toxicity resolves, the therapy should not be restarted. Oral corticosteroids must be maintained at baseline doses during Induction Study 1 and Induction Study 2, and all participants must begin tapering oral corticosteroids at Week M-0 of the Maintenance Study, unless medically not feasible (for additional details, see Section 6.5.1).

Enrolled participants should not **initiate** any of the following concomitant UC-specific medical therapies at any time during any of the 3 studies:

- Oral or rectal 5-ASA compounds.
- Oral, parenteral, or rectal corticosteroids, including budesonide and beclomethasone dipropionate.
- 6-MP, AZA, or MTX.
- Antibiotics as a primary treatment for UC.
- Total parenteral nutrition or enteral nutrition as a treatment for UC.

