If the above medical therapies are initiated or medication doses are changed based on medical necessity as assessed by the investigator, participants should continue to attend all study visits and have all assessments. While this does not represent a deviation from the study protocol, and the participants may remain on their assigned study intervention, participants who initiate or increase the dose above baseline of these UC medications during induction (ie, Induction Study 1 or Induction Study 2) will not be eligible to enter the Maintenance Study. Treatment failures due to UC medication changes will be defined in the SAP.

Laxatives should generally be avoided and should be used only in preparation for endoscopy or other procedures.

The sponsor must be notified in advance (or as soon as possible thereafter) of any changes in concomitant therapy as noted above.

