9.4.2.3.2. Primary Endpoint Analysis

The primary endpoint is clinical remission at Week M-44, defined as a stool frequency subscore of 0 or 1, a rectal bleeding subscore of 0, and an endoscopy subscore of 0 or 1 with no friability present on the endoscopy, where the stool frequency subscore has not increased from induction baseline. The analyses will be based on the Randomized Full Analysis Set.

Participants who have a colectomy or ostomy, have protocol-prohibited medication changes (to be defined in the SAP), have a dose adjustment, or who have discontinued study intervention due to any reasons other than COVID-19 related reasons or a regional crisis, including unsatisfactory therapeutic effect or an AE of worsening UC before the Week M-44 visit will be considered not to be in clinical remission at Week M-44. For participants who discontinued study intervention due to COVID-19 related reasons (excluding COVID-19 infection) or regional crisis, their observed clinical remission status at Week M-44 will be used if available. After accounting for the treatment failure rules, participants who are missing any or all of the 3 Mayo subscores that compose the modified Mayo score or who do not return for evaluation at Week M-44 will be considered not to be in clinical remission.

A precise description of the treatment effect to be estimated from the study will be described in the estimand framework. The primary estimand will use a hybrid strategy for the intercurrent events. Details on the primary estimand and other estimand definitions will be described in the SAP.

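### SAP Attachment 2 has no intercurrent-event rule for antibiotics or nutritional therapy started to treat UC, so a participant rescued this way can be scored as a remitter

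*SAP*

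**What the plan says.** Protocol Section 6.5 says that enrolled participants should not start "any of the following concomitant UC-specific medical therapies at any time during any of the 3 studies". The five listed items are 5-ASA compounds, corticosteroids, 6-MP/AZA/MTX, "Antibiotics as a primary treatment for UC" and "Total parenteral nutrition or enteral nutrition as a treatment for UC". If one is started out of medical necessity, the protocol is permissive: "While this does not represent a deviation from the study protocol, and the participants may remain on their assigned study intervention". On scoring it says: "Treatment failures due to UC medication changes will be defined in the SAP". Protocol Section 9.4.2.3.2 repeats this for the primary endpoint. Participants who "have protocol-prohibited medication changes (to be defined in the SAP), have a dose adjustment", or who have one of the other listed events, are treated as not in remission at Week M-44.

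The SAP takes this up in Section 5.3.2. ICE 3 is a prohibited change in UC medication, defined by reference to Attachment 2 alone and handled by the composite strategy. The first bullet of Attachment 2 is "Initiation of prohibited medications or therapies as defined in the protocol (see protocol Section 6.5.2". The remaining bullets deal with rectal 5-ASA and parenteral or rectal corticosteroids, then with oral corticosteroids, oral 5-ASA and 6-MP/AZA/MTX.

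**The concern.** The primary estimand treats a switch to other UC treatment as an unfavourable outcome. For that to work, the list behind ICE 3 has to reach the treatments that the protocol itself regards as UC therapy. Two of its five classes have no rule at all. The protocol plainly takes both seriously: inclusion criterion 10 (items i and j) requires a two-week washout of each, and starting either during induction bars entry to the Maintenance Study (Section 6.5).

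The result is uneven scoring within one protocol list. A participant who starts oral 5-ASA for worsening disease is a failure. One who starts an antibiotic or enteral nutrition for UC, has no other intercurrent event and meets the Mayo criteria at Week M-44 is a success.

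**Working it through.** The plan states no figure that this point disputes, so the check is mainly a comparison of the lists.

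**Step 1. Match each class in Protocol 6.5 to a scoring rule.**

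| Class in Protocol 6.5 | In Protocol 6.5.2? | Rule in SAP Attachment 2? |
|---|---|---|
| 5-ASA, oral or rectal | No | Yes: rectal start; oral start, increase or change of compound for worsening |
| Corticosteroids | No | Yes: parenteral or rectal start; oral start or increase beyond set dose and duration limits; switches for worsening |
| 6-MP, AZA, MTX | No (expressly excepted) | Yes: start, increase or switch for worsening |
| Antibiotics primarily for UC | No | None |
| Parenteral or enteral nutrition for UC | No | None |

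Protocol 6.5.2 has four items: other immunomodulators, biologics, experimental agents, and thalidomide-type drugs. The restricted-medication bullet in Attachment 2 is a closed list of rectal 5-ASA and parenteral or rectal corticosteroids. Neither reaches the last two rows.

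**Step 2. See whether another event catches these participants (SAP 5.3.2).**

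- ICE 1 is surgical and does not apply.
- ICE 4 and ICE 6 need discontinuation of study intervention. Protocol 6.5 lets these participants continue.
- ICE 5 also needs discontinuation, and it uses the observed outcome.
- ICE 2 needs a dose adjustment, sham included. That follows confirmed loss of response and can occur only from Week M-8 to Week M-32 (Protocol 4.1.3.1 and 6.6.1; SAP 1.3.1).

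**Step 3. Identify who is left.** Three routes avoid ICE 2: rescue without confirmed loss of response; worsening after Week M-32; and a later flare when the first did not confirm loss of response, since Protocol 4.1.3.1 gives no second evaluation.

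**Step 4. Look for a planned analysis that would show it.** SAP 5.4.1.2 applies the same ICE rules to the major secondary endpoints. Estimand 2 reuses Attachment 2, and Estimands 3 to 5 keep the primary ICE rules (SAP 5.3.2.3). The sensitivity analyses work after those rules have been applied. SAP 5.8 suspends ICE 2, so there even the dose-adjusted participants are no longer caught by it.

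**Step 5. Scale.** Inputs from SAP Section 3 and Table 3: 161 per arm, 25% placebo, 45% guselkumab 200 mg q4w. As a check that these are read as the plan uses them, the pooled chi-square power is

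Φ[(0.20·√161 − 1.96·√(2·0.35·0.65)) / √(0.25·0.75 + 0.45·0.55)] = Φ[(2.538 − 1.322)/0.660] = Φ(1.84) = 96.7%,

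which agrees with the stated 97%.

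One participant is 100/161 = 0.62 points of an arm's rate. The documents give no rescue frequency, so the shares below are assumptions. Let a and b be the percentages of the placebo and guselkumab arms scored as extra remitters. The apparent difference is (45 + b) − (25 + a):

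| a (placebo) | b (guselkumab) | Participants (161 × share) | Difference, points |
|---|---|---|---|
| 0 | 0 | 0 and 0 | 20 |
| 1 | 1 | 1.6 and 1.6 | 20 |
| 2 | 0 | 3.2 and 0 | 18 |
| 5 | 2 | 8.1 and 3.2 | 17 |
| 0 | 2 | 0 and 3.2 | 22 |
| 0 | 3 | 0 and 4.8 | 23 |

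The sign depends only on which arm uses more of this rescue.

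**The case against.** The best case for the plan has three parts.

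First, ICE 2 is a substantial safeguard. A first flare up to Week M-32 calls for endoscopy. Confirmed loss of response within the window leads to a dose adjustment and so to non-remission, whatever else is given. A participant who declines the endoscopy is discontinued and falls under ICE 4 or 6. This stands, and it narrows the gap to the three routes in Step 3. It does not close them, and worsening after Week M-32 is the nearest to the endpoint.

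Second, the protocol hands the definition to the SAP, and Attachment 2 is selective even within the classes it covers: short courses of oral corticosteroid, or 5-ASA started for reasons other than worsening, are not ICE 3. So absence from ICE 3 is not an error in itself. But for those classes the SAP sets a rule and a threshold, whereas for these two it is silent, although Protocol 6.5 already confines both to use as UC treatment. SAP Appendix 2 reports no change to the protocol-planned analyses, and no reason for leaving them out is given.

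Third, these therapies are discouraged rather than strictly forbidden, since a medically necessary start is not a deviation. That is correct, and it is also why no discontinuation event follows automatically.

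Two wider readings are tempting but fail. One is that such a participant succeeds on every major secondary endpoint. Only the ICE rule is shared: histologic healing, the IBDQ and fatigue thresholds, endoscopic normalization and the steroid-free period each have their own criteria, and maintenance of remission applies only to those in remission at maintenance baseline. The other is that apheresis is a further omission. Protocol 5.2 excludes "Apheresis (eg, Adacolumn or Cellsorba apheresis) within 2 weeks before the first dose of study intervention", but that is an entry criterion. Apheresis is named in neither 6.5 nor 6.5.2, so there is no mismatch between protocol and SAP to correct.

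**Conclusion.** The gap is real but narrow. Two of the five therapy classes in Protocol 6.5 have no ICE 3 rule, and the other intercurrent events do not reliably cover them. A participant rescued outside ICE 2 who meets the Mayo criteria at Week M-44 is counted as a remitter, against the stated composite strategy.

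The size is unknown and probably small. Each case is worth 0.62 points at 161 per arm, and the 17 to 23 point range above rests entirely on assumed shares.

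A reader might infer that rescue is commoner after withdrawal to placebo, and hence that the difference is biased toward zero and power is lost. The documents do not support this. They give no rescue rates by arm, and if placebo participants flare more, ICE 2 also removes more of them. Five such participants on placebo and none on guselkumab, for example, would mean 5 of about 45 counted placebo remitters (161 × 0.25 ≈ 40, plus 5), and nothing in the plan points to that. The case for the change is consistency of the estimand, not a demonstrated loss of power.

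**What to change.** Before unblinding, add two bullets to SAP Attachment 2 as ICE 3: initiation after maintenance baseline of "Antibiotics as a primary treatment for UC", and initiation after maintenance baseline of "Total parenteral nutrition or enteral nutrition as a treatment for UC". Plan a table of the use of both by treatment arm, so that their frequency can be seen.

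The data are already collected: Protocol 6.5 requires every concomitant therapy to be recorded with its treatment period and indication. The cost is two lines and one table, and a few more participants may be scored as failures. Only outcome scoring changes; what sites may give does not. If the two classes were left out on purpose, the SAP should say so and give the reason.

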6.5.1. Corticosteroids

As mentioned in Section 6.5, oral corticosteroids for UC **should not be initiated or have the dose increased above baseline** during all 3 studies. The one exception is that participants may

transiently (ie, for ≤ 4 weeks) use increased doses of corticosteroids **for reasons other than** worsening of UC (eg, stress doses of corticosteroids for surgery, asthma flare, adrenocortical insufficiency) during the Maintenance Study.

For participants who are receiving oral corticosteroids on entry into the Maintenance Study, the investigator must begin tapering the daily dose of corticosteroids beginning at Week M-0 (Table 5). Tapering of the daily dose of corticosteroids may be paused for participants meeting clinical flare criteria as described in Section 4.1.3.1. For participants whose corticosteroid taper is interrupted, investigators are encouraged to resume tapering within 4 weeks if clinically appropriate. Tapering may exceed this schedule only if warranted by medical necessity (eg, participant experiencing corticosteroid-related side effects).

Table 5: Recommended Tapering Schedule for Oral Corticosteroids	
Recommended Tapering Schedule for Oral Corticosteroids (Other than Oral Budesonide and Oral Beclomethasone dipropionate)	
Dose >15 mg/day prednisone or equivalent:	Taper daily dose by 5 mg/week until receiving 10 mg/day, then continue tapering by 2.5 mg/week until 0 mg/day
Dose 11 to 15 mg/day prednisone or equivalent:	Taper daily dose to 10 mg/day for 1 week, then continue by 2.5 mg/week until 0 mg/day
Dose ≤ 10 mg/day prednisone or equivalent:	Taper daily dose by 2.5 mg/week until 0 mg/day
Recommended Tapering Schedule for Oral Budesonide and Oral Beclomethasone dipropionate	
Participants receiving oral budesonide or oral beclomethasone dipropionate should have their daily dose tapered according to local clinical practice until 0 mg/day.	

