5.3.2. Primary Estimand (Estimand 1)

The primary estimand, i.e., a precise definition of the primary targeted treatment effect is defined by the following 5 attributes:

Randomized Maintenance Treatment by Week M-44:

Experimental:

- Guselkumab 200 mg SC q4w
- Guselkumab 100 mg SC q8w

Control:

• Placebo SC

Population: Patients 18 years or older with moderately to severely active UC as reflected in the inclusion/exclusion criteria (Protocol Section 5) along with a requirement of a modified Mayo score of 5 to 9 who were induced into clinical response with guselkumab.

Variable: Clinical remission at Week M-44 (Section 5.3.1.) where participants are considered to have achieved clinical remission if they fulfill the clinical remission criteria based on modified Mayo score components (Section 5.3.1.1.), and do not experience intercurrent events in categories 1-4 and 6 (defined below) prior to the Week M-44 visit.

Intercurrent Events and Corresponding Strategies:

The following are the intercurrent events for this study:

- 1. An ostomy or colectomy (partial or total)
- 2. Have a dose adjustment (including a sham dose adjustment; Section 1.3.1)
- 3. Prohibited change in UC medication (described in Attachment 2)
- 4. Discontinuation of study intervention due to lack of efficacy or an AE of worsening of UC
- 5. Discontinuation of study intervention due to major disruption, including COVID-19 related reasons (excluding COVID-19 infection) or regional crisis in Russia and Ukraine
- 6. Discontinuation of study intervention due to reasons other than those in ICEs 4 and 5

Intercurrent events (ICEs) in categories 1-4 and 6 will be handled with the composite strategy as reflected in the variable definition. ICE category 5 will be handled by the Treatment Policy Strategy. Note that the application of ICE categories 1-3 overrides that of ICE 5. This means that a participant with ICE in categories 1-3 will be considered as not to have achieved the variable, regardless of whether the participant has had an ICE 5. For participants experiencing ICE 5, their observed clinical remission status (if available) at Week M-44 will be used.

Population-level summary:

The difference in the proportion of participants achieving the variable (as defined above for this estimand) between each guselkumab group and the placebo group.

Note: This estimand acknowledges that having an intercurrent event in categories 1-4 and 6 is an unfavorable outcome.

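### SAP Attachment 2 counts any parenteral corticosteroid start as ICE 3, whatever its reason or length, while a short oral course for the same non-UC reason is not counted

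*SAP*

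**What the plan says.** SAP Attachment 2 opens by stating: "Participants who had a prohibited change in UC medication described below are considered to have ICE 3". One bullet in its list reads "Initiation of restricted medications (rectal 5-ASA compounds; parenteral or rectal corticosteroids, including budesonide and beclomethasone dipropionate". It carries no reason, dose or duration.

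The bullets for oral corticosteroids, oral budesonide and oral beclomethasone are conditional. Increases have a dose threshold. An increase or new start due to worsening disease counts after more than 7 days. One due to anything else counts only if it lasts "for more than 28 days after the maintenance baseline visit due to reasons other than worsening of disease".

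Protocol Section 6.5 says that participants should not start "any of the following concomitant UC-specific medical therapies at any time during any of the 3 studies", and parenteral corticosteroids are on that list. Section 6.5.1 sets one exception for the Maintenance Study: for up to 4 weeks participants may "use increased doses of corticosteroids" when UC is not the cause. Its examples include surgical stress doses and an asthma flare. No route is given. On scoring, Protocol Section 6.5 says: "Treatment failures due to UC medication changes will be defined in the SAP".

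SAP Section 5.3.2 states: "Intercurrent events (ICEs) in categories 1-4 and 6 will be handled with the composite strategy as reflected in the variable definition". SAP Section 5.4.1.2 carries the same strategies to every major secondary endpoint.

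**The concern.** The composite strategy treats ICE 3 as an unfavourable UC outcome. A single parenteral dose given around surgery says nothing about UC, yet the bullet turns a participant who meets every remission criterion at Week M-44 into a non-remitter. The same drug class given by mouth for the same reason, for up to 28 days, leaves that participant a remitter. The SAP gives no reason for separating the two by route.

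At stake is whether the primary endpoint means what the estimand says it means, and whether two programmers would derive ICE 3 alike from this text.

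**Working it through.** **1. The rules side by side, for a non-UC reason in the Maintenance Study**

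| Situation | Source | Scored as ICE 3? |
|---|---|---|
| New oral course, 28 days or less | SAP Attachment 2, oral bullets | No |
| New oral course, more than 28 days | SAP Attachment 2, oral bullets | Yes |
| One parenteral dose | SAP Attachment 2, restricted-medication bullet | Yes |

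The SAP's 28 days equal the protocol's 4 weeks (4 × 7 = 28). The oral bullets therefore match the length of the Section 6.5.1 allowance; the parenteral wording has no such allowance.

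**2. Does the header exempt non-UC use?** It speaks of UC medication, but it also governs the oral bullets that deal explicitly with reasons other than worsening disease. It therefore does not remove non-UC use from the list.

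**3. Would any planned analysis show the effect?**
- Estimand 2 keeps ICE 3 composite, and Estimands 3-5 inherit the primary ICE strategies. Estimands 6-9 do the same for the major secondary endpoints.
- The tipping-point and multiple-imputation analyses act after the ICE rules. The source-data-verification analyses keep the same strategies.
- Section 5.8 suspends ICE 2 only. Section 5.7 drops the ICE strategies, but only to describe dose-adjusted participants, and clinical remission is not among its endpoints.
- Section 5.5 plans a count of participants with intercurrent events, but does not say that it will be split by type of medication change.

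**4. Size.** Inputs from SAP Section 3: remission 25% on placebo and 45% on guselkumab; about 161 per group with stated power 97%; 118 per group with stated power 90%; two-sided 0.05.

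Power = Φ{[Δ√n − 1.96√(2p̄(1−p̄))] / √(p₁(1−p₁) + p₂(1−p₂))}, with Δ = 0.20 and p̄ = 0.35.
- n = 161: (2.538 − 1.322)/0.6595 = 1.843, power 96.7% (plan: 97%).
- n = 118: (2.173 − 1.322)/0.6595 = 1.290, power 90.1% (plan: 90%).

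Both planned figures reproduce. Now let a share f of remitters be reclassified. The documents give no incidence, so f is assumed; if 1-4% of each arm receive such a dose independently of remission status, f is 1-4%.
- Guselkumab: 161 × 0.45 × f = 0.7 participants (f = 1%) to 2.9 (f = 4%).
- Placebo: 161 × 0.25 × f = 0.4 to 1.6.
- Loss in the difference: 20 points × f = 0.2 to 0.8 points.

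Power at 161 per group, over a slightly wider range:

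| f | Both arms affected | Guselkumab remitters only |
|---|---|---|
| 0% | 96.7% | 96.7% |
| 1% | 96.5% | 96.1% |
| 2% | 96.3% | 95.3% |
| 5% | 95.5% | 92.4% |

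**5. Direction.** The difference changes by −45 × f(guselkumab) + 25 × f(placebo) points. It shrinks unless the placebo share exceeds 45/25 = 1.8 times the guselkumab share. Nothing in the documents suggests such an imbalance.

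**6. Secondary endpoints.** The loss scales with each assumed difference in SAP Table 3. For endoscopic normalization (18% vs 29%) it is 11 × f = 0.11-0.44 points; for fatigue response (26% vs 55%) it is 29 × f = 0.29-1.16 points. Corticosteroid-free remission requires 8 steroid-free weeks before Week M-44, so a dose in that window fails it with or without ICE 3.

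**The case against.** A reader might infer that the protocol expressly permits parenteral non-UC use and that the SAP contradicts it on what counts as treatment failure. The documents do not go that far. The Section 6.5.1 exception follows a sentence about oral corticosteroids and speaks of increased doses, not of starting a parenteral agent. Reading it as covering a parenteral start is plausible, because surgical stress doses are its first example and no route is named, but it is an inference. Permission and scoring are also separate matters: Protocol Section 6.5 says that medically necessary starts are not deviations and still leaves the definition of failure to the SAP. No protocol text says that use under Section 6.5.1 must not be scored as failure.

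The strict rule could also be deliberate. Attachment 2 treats prohibited and restricted agents alike, by any initiation, and an unconditional rule avoids judging the reason for treatment. The planning rates come from an earlier sponsor trial; if its failure rules were similar, they may already include some of this loss.

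These points remove the charge of an express contradiction and lower the weight. They do not explain why the SAP judges reason and duration for oral corticosteroids but not for parenteral ones. If the strict rule was intended, nothing says so, and no analysis shows what it costs.

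**Conclusion.** The point holds as an unexplained inconsistency by route: within Attachment 2 itself, and between its parenteral wording and the transient non-UC allowance in Protocol Section 6.5.1. On the literal text, a true remitter becomes a failure for short non-UC treatment.

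The effect is small: 0.2-0.8 points off a 20-point difference if 1-4% per arm are affected. That rate is an assumption, as are independence from remission status and similar shares in the arms. A reader might infer a threat to power or a bias in favour of guselkumab. The figures support neither: power stays above 92% even with 5% of guselkumab remitters alone reclassified, and with similar shares in both arms the effect works against guselkumab. It is also not uniform across the major secondary endpoints. The reason to act is the clarity of the primary endpoint definition, not the size of the effect.

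**What to change.** Before unblinding, reconcile the parenteral part of the bullet with Protocol Section 6.5.1 and with the SAP's oral bullets, for endpoint scoring only:

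- Separate parenteral corticosteroids from the rectal agents, and leave the rectal rules unchanged.
- Keep any parenteral start for worsening disease as ICE 3, as now. This is deliberately stricter than the oral rule, which requires more than 7 days.
- Score parenteral starts for other reasons by the non-UC allowance that the SAP already applies to oral corticosteroids.

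If the unconditional rule is intended, state that in Attachment 2 and add a supplementary analysis of the primary and major secondary endpoints that does not count short non-UC parenteral use as ICE 3.

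The cost is one SAP bullet and its programming, or one added analysis. No new data are needed: Protocol Section 6.5 already requires route, treatment period, dosage and indication to be recorded. The downside is that scoring then relies on the recorded indication, as the oral bullets already do. None of this changes what participants may receive, and no view is taken on the clinical rule.
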